4.4 Month derivation

For all derivations, a month will be calculated as $(365.25 / 12) = 30.4375$ days. If duration is to be reported in months, duration in days will be divided by 30.4375.

4.5 Age derivation

Age will be calculated based on the date when the patient signed the main study informed consent from the date of birth.

4.6 Dose interruptions and dose changes

This section provides additional details to those included in [Section 2.6](#).

All reporting of dose interruptions and dose changes are based on the dose actually taken by the patient and flags for dose interruption/change recorded on the [DAR] eCRF page.

An interruption is defined as a 0 mg dose taken on one or more days. What follows defines how dose interruptions will be counted in the case of multiple dose interruptions.

- If an interruption occurs consecutively for at least two days due to the same reason, then it will be counted only once (*example: If the actual dose on days 1-3 is 750 mg and actual dose on days 4-5 is 0 mg and dose interruption on days 4-5 is due to AE, then the total number of dose interruptions is 1*).

A dose change is defined as a change in dosing from one record to the next; however a dose interruption will not be counted as a dose change.

Dose reductions are a subset of dose changes where dose changes to higher than protocol planned dose are excluded.

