6.3.2 Treatment interruption and treatment discontinuation

If the administration of LDK378 is temporarily interrupted for reasons other than toxicity, then treatment with LDK378 may be resumed at the same dose. The same applies if the patient experiences an unacceptable toxicity not specifically described in [Table 6-3](#), provided this toxicity resolved to \leq CTCAE grade 1.

If the treatment with LDK378 is withheld due to toxicity, scheduled visits and all assessments should continue to be performed (with the exception of the dosing of the withheld study drug), as described in [Table 7-1](#).

If the treatment with LDK378 dosing is withheld for more than 28 consecutive days (counting from the first day when a dose was missed), due to treatment-related toxicity, then LDK378 should be permanently discontinued except in cases where the investigator believes the patient continues to derive clinical benefit. In such cases, treatment with LDK378 may be resumed at a lower dose.

Detailed guidelines for follow-up of study drug related AE or an abnormal laboratory value must be followed as described in [Section 6.3.4](#).

All patients will be followed for safety until 30 days after the last dose of LDK378. Patients whose treatment is temporarily interrupted or permanently discontinued due to an AE or abnormal laboratory value must be followed until resolution or stabilization of the event, whichever comes first, including all study assessments appropriate to monitor the event.

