10.5.3.5 Tolerability

Tolerability will be evaluated in terms of dose reductions or drug interruptions due to an AE.

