Average daily dose (mg/day):	$\text{Cumulative dose (mg)} / \text{Number of dosing days}$
Dose intensity; DI (mg/day):	$\text{Cumulative dose (mg)} / \text{Duration of exposure (days)}$
Relative dose intensity; RDI (%):	$100 \times \text{DI (mg/day)} / \text{Planned dose (i.e., 750 mg/day)}$

Note:

Given the planned dose of 750 mg/day, the planned dose intensity (PDI) can be calculated as:

$\text{PDI (mg/day)} = \text{Cumulative planned dose (mg)} / \text{Duration of exposure (days)}$,

where

$\text{Cumulative planned dose (mg)} = \text{Planned dose of 750 (mg)} \times \text{Duration of exposure (days)}$.

Then, RDI (%) which is calculated as $(100 \times \text{DI} / \text{PDI})$ can be simplified as shown above.

Duration of exposure to study drug, cumulative dose, average daily dose, DI and RDI will be summarized. In addition, the duration of exposure to study drug and RDI will be categorized and the frequency counts and percentages of patients in each category will also be presented.

Frequency counts and percentages of patients who have dose changes, reductions or interruptions, and the corresponding reasons, will be summarized. In addition, descriptive statistics will also be presented for the % of actual days dosed, % of days received full dose, number of dose changes, and number of dose interruptions.

Time to first dose reduction, defined as the time from the first dose of study drug to the first reduction of study drug, will be summarized in 2 month-intervals. Summary statistics of time to first dose reduction will also be presented. Time to first dose interruption, defined as the time from the first dose of study drug to the first interruption of study drug, will be summarized in a similar way.

Listings of all doses of the study drug along with dose change and dose interruption reasons will be produced. The derived exposure variables will also be listed by patient.

[Section 4.6](#) provides further details on the definition of dose changes and interruptions.

Concomitant therapy

Concomitant therapies are defined as any medications (excluding study drug, prior antineoplastic treatments and blood transfusions), surgeries or procedures (including physical

therapy) administered in the study and are recorded in the [Prior and Concomitant Medications] and the [Surgical and Medical Procedures] eCRF pages, respectively.

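### The SAP's definition of a dose reduction does not require the dose to go down, and it leaves open whether a same-dose restart after an interruption counts as one

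*SAP*

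**What the plan says.** SAP 4.6 bases reporting on the dose the patient actually took, together with interruption and change flags on the dosing eCRF page. It then builds three definitions on one another:

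- Interruption: "An interruption is defined as a 0 mg dose taken on one or more days".
- Dose change: "A dose change is defined as a change in dosing from one record to the next", with the proviso "however a dose interruption will not be counted as a dose change".
- Reduction: "Dose reductions are a subset of dose changes where dose changes to higher than protocol planned dose are excluded".

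The planned dose is 750 mg/day (SAP 2.6, Table 2-1).

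SAP 2.6 uses these definitions for the counts and percentages of patients with changes, reductions and interruptions, for the reasons, for the number of dose changes, and for time to first reduction: "Summary statistics of time to first dose reduction will also be presented". Protocol 10.5.3.5 adds: "Tolerability will be evaluated in terms of dose reductions or drug interruptions due to an AE".

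On restarts, protocol 6.3.2 says of interruptions for reasons other than toxicity: "then treatment with LDK378 may be resumed at the same dose". It extends this to some toxicities not listed in Table 6-3. Several rows of Table 6-3 also keep the dose level after an interruption: grade 4 neutropenia, grade 3 thrombocytopenia, grade 2 bilirubin and grade 2 creatinine when each resolves within 7 days, and a first episode of grade 2 diarrhea or vomiting.

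**The concern.** A reduction is normally a step down. The SAP's filter instead removes only changes that end above 750 mg and keeps every other change, whichever way it goes. That is an error of wording whatever is done with 0 mg records.

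The second problem is a gap. The proviso says an interruption is not a dose change, but the record after the interruption is a non-zero dose that differs from the 0 mg record before it. The SAP does not say whether that restart is compared with the 0 mg record or with the last non-zero dose. Its only worked example stops while the dose is still 0 mg.

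Two programmers could therefore produce different reduction tables from the same text. A patient who paused and resumed at 750 mg could appear as dose-reduced, with the first reduction dated at the restart.

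**Working it through.** This is a check of a counting rule, so the rule was applied to short dose sequences.

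**Inputs.** The three definitions and the use of doses actually taken are from SAP 4.6. The planned dose of 750 mg/day is from SAP 2.6. N = 20 is from SAP 2.9.

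**Rules compared.**

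- Reading A: compare adjacent records, and exempt only the move into 0 mg.
- Reading B: treat the 0 mg block as the interruption, skip it, and compare successive non-zero doses.
- Under both, a reduction is any counted change that ends at 750 mg or less.
- Directional rule: a non-zero dose lower than the last preceding non-zero dose.

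**The SAP's own example.** 750 mg on days 1–3 and 0 mg on days 4–5 gives 1 interruption, as the SAP states, and 0 reductions under both readings. It does not test the restart.

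**Number of reductions by sequence (mg).**

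| Sequence | Reading A | Reading B | Directional |
|---|---|---|---|
| 750–600 | 1 | 1 | 1 |
| 750–0–600 | 1 | 1 | 1 |
| 750–0–750 | 1 | 0 | 0 |
| 750–600–0–600 | 2 | 1 | 1 |
| 600–750 (partial first dose) | 1 | 1 | 0 |
| 750–600–750 | 2 | 2 | 1 |
| 750–450–600 | 2 | 2 | 1 |
| 750–900–750 | 1 | 1 | 1 |

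**Upward steps.** These count as reductions under both readings. If the first record is 750 mg and 0 mg records are skipped, an upward step to 750 mg or less can only follow an earlier step down or a dose above plan. It then adds to the count and the reasons, but the patient already had a counted reduction. The exception is a first record below 750 mg: 600–750 produces a first reduction on day 2 where there was none. Protocol 6.1.1 foresees partial doses, so such a record is possible.

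**Restarts.** With 750 mg on days 1–3, 0 mg on days 4–5 and 750 mg from day 6, Reading A dates a first reduction on day 6 and Reading B finds none. Under Reading A, a patient who restarts at the same dose and is truly reduced later is rightly counted as reduced, but time to first reduction is measured to the restart.

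**Size.** If k patients with no true reduction are misclassified, the percentage rises by 100 × k/20 = 5k points. The documents do not give k. Assuming 0 to 8 such patients, the range is 5 × 0 = 0 to 5 × 8 = 40 points. Under Reading B the contribution from restarts is 0 for any number of restarts.

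**The case against.** The strongest reply is that the proviso already settles the matter. SAP 4.6 describes an interruption as lasting one or more days and takes it out of dose changes. Setting the whole 0 mg block aside and comparing the doses on either side is a natural reading, and it gives no reduction for 750–0–750. The eCRF flags could also separate a resumption from a change, and protocol Table 6-2 uses reduction in its ordinary downward sense. This stands as far as it goes: the text permits that reading. It does not state it, and it does not say how flags and recorded doses combine.

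It is also fair that protocol 6.3.3 bars re-escalation, so 450-to-600 mg steps should be rare deviations and usually leave patient-level results unchanged.

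The combined tolerability measure in protocol 10.5.3.5 is protected too: a patient who paused for an adverse event qualifies through the interruption whether or not the restart is miscounted. SAP 2.8.2 separately tabulates adverse events requiring dose adjustment, interruption, or either, and is not stated to use the SAP 4.6 definition for this.

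None of this supplies the missing direction in the definition or classifies the restart.

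**Conclusion.** The definition needs correcting. Under both readings it classes upward steps to 750 mg or less as reductions. On a literal record-to-record reading it also classes same-dose restarts as reductions. The outputs at risk are those in SAP 2.6: patients with a reduction, their reasons, the number of dose changes, and time to first reduction. The effect on the percentage is 5 points per misclassified patient at N = 20, with no restart error if 0 mg records are skipped. ORR, the other efficacy endpoints and the sample-size figures do not depend on it.

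A reader might infer that every patient who pauses and resumes at the same dose will be reported as dose-reduced. The documents do not support that, because skipping 0 mg records or using the flags would avoid it. Nor do they show that a comparison with the 61.8% of phase I patients with reductions due to adverse events (protocol 1.2.1.2.1) would be spoiled: no such comparison is planned, and it is not known that restart records would carry an adverse-event reason.

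A reader might also see the lack of a Kaplan-Meier analysis of time to first reduction as an error. In a descriptive study with no hypothesis testing, that is a preference.

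**What to change.** In SAP 4.6, define a dose reduction as a non-zero dose lower than the last preceding non-zero dose, skipping 0 mg records. State that resuming at the same dose after an interruption is neither a dose change nor a reduction. Say how the eCRF flags and the recorded doses are combined when they disagree. Use the one definition for the counts, the reasons and time to first reduction in SAP 2.6.

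Two cases remain for the sponsor to settle in the same edit, since doses actually taken are used: a single partial-dose day (750–600–750), and a return to plan from a dose above it (750–900–750). Each still counts as one reduction under the directional rule.

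The cost is a few sentences and a small programming change before database lock, with no new data collection.

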4.7 Efficacy endpoints

For further details on efficacy endpoints, see Section 15 (Appendix 2) of the CLDK378A1201 protocol. For the evaluation of tumor-response related endpoints, response is assessed by investigator according to RECIST 1.1.

Response and progression evaluation will be performed according to the Novartis RECIST 1.1 guidelines, included in Section 15 (Appendix 2) of the protocol.

The text below gives more detailed instructions and rules needed for programming of the analyses described in [Sections 2.7](#) and [2.8.1](#).

4.7.1 Implementation of RECIST guidelines

Disease progression

PD should only be assigned if it is confirmed by an objective assessment method as per RECIST 1.1 (e.g., radiologic scan, histology for bronchoscopy, photos for skin lesions). If a new lesion is detected using an objective assessment method other than radiologic scan, it should be entered on the [RECIST New Lesion] eCRF page with appropriate method (or method='Other').

In particular, discontinuation due to disease progression or death due to progressive disease, without supporting objective evidence (as defined above), will not be considered as PD in the determination of BOR, the derivation of any efficacy endpoint or efficacy analysis.

Change in imaging modality

Per RECIST 1.1, a change in methodology can be defined as either a change in contrast use (e.g., keeping the same technique, like CT, but switching from with to without contrast use or vice-versa, regardless of the justification for the change) or a change in technique (e.g., from CT to MRI, or vice-versa), or a change in any other imaging modality. A change from conventional to spiral CT and vice versa while keeping same contrast use (e.g., switching from spiral CT with contrast to CT with contrast) is not considered a change in imaging modality. A change in methodology will result by default in an UNK (unknown) overall lesion response assessment. However, a response assessment other than the Novartis calculated UNK response may be accepted from the investigator if a definitive response assessment can be justified based on the available information. Potential discrepancies between the modality used and overall lesion response reported by the investigator (e.g., change in modality but investigator assessment of response is different from UNK) will be queried during the data review process.

Determination of missing adequate tumor assessments

For the computation of ORR, patients without any radiological assessment after the start date of study drug will be counted as failure.

Partial or complete responses reported prior to any additional anticancer therapy will be considered for ORR computation irrespective of the number of missed assessments before response. In this section, the ‘missing adequate assessment’ is defined as assessment not done or assessment with overall lesion response equal to UNK. For the sake of simplicity, the ‘missing adequate assessment’ will also be referred as ‘missing assessment’.

As detailed in Section 15 (Appendix 2) of the protocol, the PFS censoring and event date options depend on the presence and the number of missing tumor assessments. *For example, an event occurring after two or more missing assessments is censored in the analysis of PFS at the last adequate tumor assessment before the event date.*

An exact rule to determine whether there is none, one or two missing assessments is therefore needed. This rule will be based on the distance between the last adequate tumor assessment date and the event date.

If the distance is larger than threshold D_1 or D_2 then the analysis will assume one or two missing assessments, respectively. The threshold D_1 will be defined as the protocol specified interval between the tumor assessments plus the protocol allowed window around the assessments. Similarly, the threshold D_2 is defined as two times the protocol specified interval between the tumor assessments plus the protocol allowed window around the assessments. In this study, the protocol defined schedule of tumor assessment is every 8 weeks and each assessment is expected to be performed at the scheduled time point plus or minus 1 week, i.e., the window is 2 weeks, then any distance larger than $D_1 = 8 + 2 = 10$ weeks means one missing assessment and any distance larger than $D_2 = (8 \times 2) + 2 = 18$ weeks means two missing assessments.

The same definition of D_2 will be used to determine the PFS censoring reason.

Possible censoring reasons for PFS are:

1. Ongoing without event
2. Lost to follow-up
3. Withdraw consent
4. Adequate assessment no longer available
5. New cancer therapy added prior to disease progression
6. Event after ≥ 2 missing tumor assessments

PFS censoring reason is then derived by the following sequence of rules.

- If patient is considered to have a PFS event then PFS censoring reason is set to missing.
- Else if patient has had no baseline tumor assessment then PFS censoring reason = 4.
- Else if start date of new anti-neoplastic therapy is before any PFS event which is less than D_2 distance after date of last adequate tumor assessment (LATA), i.e., if $(\text{PFS event date} - \text{LATA date}) \leq D_2$, then PFS censoring reason = 5.
- Else if patient has a PFS event after two or more missing assessments, i.e., if $(\text{PFS event date} - \text{LATA date}) > D_2$ and PFS event is before min date, then PFS censoring reason = 6.
- Else if min date = date of withdrawal of consent and $(\text{date of withdrawal of consent} - \text{LATA date}) \leq D_2$ then PFS censoring reason = 3.

- Else if min date = date of treatment discontinuation and (date of treatment discontinuation – LATA date \leq D₂) and date of discontinuation reason in the [End of Treatment Phase Disposition] eCRF page = ‘Lost to follow-up’ then PFS censoring reason = 2.
- Else if min date = analysis cut-off date and (analysis cut-off date – LATA date \leq D₂) then PFS censoring reason = 1.
- Else PFS censoring reason = 4.

where min date = minimum of non-missing (analysis cut-off date, start date of further anti-neoplastic therapy, date of withdrawal of consent, date of discontinuation due to loss to follow-up).

Non-measurable disease at baseline

As specified in Section 15 (Appendix 2) of the protocol, the RECIST 1.1 criteria imply that only patients with measurable disease at baseline should be included in the study. If a patient without measurable disease is enrolled, the intent-to-treat (ITT) principle requires including these patients in the analyses. Hence, analyses will be based on the FAS including patients with either measurable or non-measurable disease. Therefore, a rule needs to be specified on how to handle these cases.

As specified in Section 15 (Appendix 2) of the protocol, overall lesion response can be derived for patients without measurable disease at baseline as follows ([Table 4-2](#)).

Table 4-2 Overall lesion response at each assessment: patients with non-target disease only

Non-target lesions	New lesions	Overall lesion response
CR	No	CR
Non-CR/Non-PD *	No	Non-CR/Non-PD
UNK	No	UNK
PD	Yes or No	PD
Any	Yes	PD

* In general, the Non-CR/Non-PD response for these patients is considered equivalent to an SD response in endpoint determination.

Missing baseline tumor assessment

As specified in Section 15 (Appendix 2) of the protocol, since the timing of PD cannot be determined for patients with missing baseline tumor assessment, these patients are censored in the PFS analysis at the start date of study drug. This rule, however, only applies to the ‘PD component’ of the PFS or DOR assessment.

Patients without baseline tumor assessment who die within D₂ distance from start date of study drug will be counted as having an event in the primary analysis of PFS. All deaths will be counted in the OS analysis regardless of presence or absence of the baseline tumor assessment.

Construction of waterfall graphs

The waterfall graphs will be used to depict the anti-tumor activity. These plots will display the best percentage change from baseline in the sum of the measured diameters of all target lesions for each patient. The proportions of patients with various degrees of tumor shrinkage or growth can then represent a useful efficacy metric.

However, caution needs to be paid to the assessments, where an occurrence of a new lesion or worsening in non-target lesions (resulting in PD as an overall lesion response at given assessment) contradicts the measurements obtained on target lesions. These assessments will not be displayed as bars in the graph. If such a 'contradicting' assessment represents the only post-baseline assessment for a patient, then the patient will be represented by a special symbol (e.g., *) in the waterfall graph.

The assessments with unknown target response and also assessments with unknown overall lesion response will be excluded. Patients without any valid assessments will be completely excluded from the graphs.

The total number of patients displayed in the graph needs to be shown and this number will be used as a denominator when calculating the percentages of patients with tumor shrinkage and tumor growth. Footnote will explain the reason for excluding some patients (due to absence of any valid assessment) as needed.

All possible assessment scenarios are described in [Table 4-3](#).

Table 4-3 Inclusion/exclusion of assessments used in waterfall graph

Criteria for inclusion/exclusion		Possible source of contradictions		
Target response	Overall lesion response	Include in waterfall	Non-target response	New lesion?
CR/PR/SD	PD	Yes but as * only	PD	Any
CR/PR/SD	PD	Yes but as * only	Any	Yes
UNK	UNK or PD	No	Any	Any
CR/PR/SD	UNK	No	UNK	No
CR/PR/SD	CR/PR/SD	Yes as a bar	Non-CR/Non-PD	No
PD	PD	Yes as a bar	Any	Any

The following algorithm will be used to construct the graph:

1. Select 'valid' post-baseline assessments to be included, i.e., for each patient and each assessment repeat the following four steps:
 - a. Check the target lesion response and overall lesion response at each assessment. If at least one of them is UNK then exclude the whole assessment. Otherwise, go to step b.
 - b. Check the overall lesion response. If PD, then go to step c. Otherwise, go to step d.
 - c. Check target response. If PD, then go to step d. Otherwise flag the assessment *.
 - d. Calculate the % change from baseline in target lesions.
2. For each patient, go through all valid assessments identified in step 1 and find the assessment with best % change from baseline in target lesions. The 'best' means best for the patient, i.e., the largest shrinkage or if a patient only has assessments with tumor

growth take the assessment where the growth is minimal. (*Example 1*: Patient 1 has the following % changes from baseline at assessments 1, 2, 3, 4 and 5, respectively: -10%; -25%; -13%; -4% and +6%. His/her best % change is then -25%. *Example 2*: Patient 2 has the following % changes from baseline at assessments 1, 2 and 3, respectively: +5%; +18% and +35%. His/her best % change is then +5%).

3. Construct the waterfall graph displaying the best % change from baseline for each patient. Patients having only * flagged assessment(s) will be displayed separately.

Investigator assessment will be used in the construction of waterfall plot.

The recommended way of the display from left to right is:

1. Bars above the horizontal axis representing tumor growth.
2. Bars under the horizontal axis representing tumor shrinkage.
3. 'Zero' bars with * symbol representing patients with contradiction.

In addition, patients with a PFS event will be represented by the flag '#' below or above the vertical bars.

